## **8. Monitoring Subject Safety and minimizing risks**

### **8.1. Risks to Subjects**

Physical risks: Physical risks to subjects include if they are offered a pain management procedure and suffer a complication of this procedure. These specific risks and benefits will be reviewed between the patient and the interventional pain management specialist, and patients will be required to sign a standard institutional informed consent document for that procedure as is customary at DFCI and all Mass General Brigham sites.

Psychological risks: Survey assessments, including reporting pain or depressive symptoms could be distressing for some patients.

Privacy risks: There is a risk of privacy violation or loss of confidentiality. This risk is anticipated to be

minimal, and the study team is committed to guaranteeing adequate protection against risk as described in the following section.

## **8.2. Protection Against Risks**

### *Recruitment and Informed Consent*

Participants will be sent a study letter and given the option to opt out of the study. If they do not opt out, participants will be approached in by the RA in a private and confidential manner. If the patient is eligible and interested in participation, the study letter and consent form will be reviewed with and signed by the participant. The RA will keep all signed documents in a password protected folder or locked cabinet, accessible only to the PI-designated study team member.

The informed consent to participate will adhere to strict standards regarding its content. Required sections include: Introduction; Why is this research study being done? What other options are there? What is involved in the research study? How long will I be in this research study? What are the risks or discomforts of the research study? What are the benefits of the research study? Can I stop being in the research study and what are my rights? What are the costs? What happens if I am injured or sick because I took part in this research study? What about confidentiality? Whom do I contact if I have questions about the research study?

### **8.2.1. Protection against the 3 types of risk to this study:**

**Physical Risks:** Physical risks would all be attributable to routine clinical care received while participating on this study. This is minimized by the fact that we are referring to an expert group of anesthesiologists who are fellowship trained in interventional pain management and all of whom have extensive experience managing cancer pain. We further mitigate any physical risks by using the treatment algorithm as a guide for management. Furthermore, we will hold bi-weekly meetings with study investigators, [name], [name], and [name] to review all patients on the study including their cancer history, pain syndrome, their candidacy for interventional procedures and outcomes. There is also a risk that patients' may feel a false sense of reassurance in reporting their symptoms on the MyPainPal application. We will mitigate this risk by including a disclaimer in the application that the

PROTOCOL TITLE: Randomized Clinical Trial of Early Intervention Pain Management for Patients with Advanced Cancers  
Version 4.0, [October 27, 2023]

reported symptoms are not monitored 24/7 and that they should contact their care team for any severe symptoms. Furthermore, any severe symptoms (e.g. pain level of 8 or greater, report of any “red flag” symptom such as fever, vomiting, obstipation) prompts the patient to call their care team immediately. Moreover, any symptoms that are poorly controlled (but not severe enough to merit an alert to contact their care team immediately) are displayed in red on the MyPainPal portal to alert the study team. The patient’s care team (oncology, anesthesia pain and palliative care if relevant) will be notified via an Epic inbasket message or email (depending upon clinic preference).

**Psychological Risks:** Study assessments use validated instruments which have been used in prior studies without causing any significant distress. Should a patient express severe psychological distress to study staff, we will contact the patients’ care team and if needed (e.g. the patient expresses suicidal ideation), the study staff will page an urgent social work consultation.

**Privacy risks:** Protection against privacy risks: To monitor the risk of loss of confidentiality/privacy, the study team has ensured that the MyPainPal app is HIPPA compliant and meet the privacy and security standards set by DF/HCC. In addition, all collected study data will be maintained in a secure location and personal identifiers will be removed.

**To maximize data security, both REDCap and MyPainPal employ:**

User Privileges - To ensure that users have access only to data and information that they are supposed to have within the application, user privileges are utilized within the software. Each user has their own account, and their user account will only have access to information that they themselves have created or to which administrators have granted them access.

Password-protection & Authentication - Both systems are password protected and implement authentication to validate the identity of end-users that log in to the system.

Auto-logout setting will automatically log a user out of the system if they have not had any activity (e.g. typing, moving the mouse) on their current web page for the set amount of time. This prevents someone else from accessing their account and their data if they leave a workstation without properly logging out or closing their browser window.

Logging and Audit Trail - Both systems maintain built-in audit trails that log all user activity and all pages viewed by every user.

## 9. Statistical Analysis and Sample Size

Power calculations are inappropriate for this pilot feasibility study. We plan to enroll 31 patients over a 6-month period, with 4 additional months for follow-up and 2 months for study preparation and data analysis – based upon projections of clinical volume.

The primary purpose of our analysis is to examine feasibility and acceptability of the intervention. Benchmarks of feasibility/acceptability are as follows

1. Proportion of patients assigned to the intervention that undergo an interventional pain consultation within 4 weeks:  $\geq 80\%$
2. Among patients referred and evaluated by an anesthesia pain specialist, at least 50% will agree and ultimately receive at least one interventional pain procedure
3. Satisfaction with the intervention: At least 80% of patients will be satisfied with the quality of care received in the interventional pain management clinic, defined as rating it a 7 or above on a 0-10 scale.

Analyses will be conducted using an intent-to-treat analysis. Pre-post differences will be assessed and univariate and multivariate descriptive analyses will be performed on all the dependent variables. Statistical significance will be set at  $p < 0.05$ . Chi-square, t-tests, and logistic regression and cluster analyses will be conducted as appropriate. We will calculate the proportion of participants meeting feasibility benchmarks with 95% confidence intervals. Pre-post differences in pain severity (primary outcome) will be examined using a one-sample t-test. One-sample t-tests will also examine pre-post differences in pain interference scores, QOL scores (using the FACT-G), QOL subscales (e.g. physical wellbeing, functional wellbeing), depression/anxiety scores, and opioid MMEs. We will also calculate the proportion of patients undergoing dichotomous outcomes (e.g. occurrence of pain-related ED visits), and the proportion alive at end-of-study. Participants will also be consented for mortality follow-up to allow for examination of survival data.

Missing data will be imputed using a last observation carried forward principle, which will be greatly enhanced by the inclusion of smartphone symptom tracking.

PROTOCOL TITLE: Randomized Clinical Trial of Early Intervention Pain Management for Patients with Advanced Cancers  
Version 4.0, [October 27, 2023]

We will fit longitudinal data on pain (derived from the smartphone-based symptom reporting) with linear regressions to estimate the trajectories in pain and to explore the effect of the intervention on pain trajectories, adjusting for each participant's baseline measure. We will also explore the association of potentially moderating variables (e.g. opioid doses, specific interventions patients have for their pain) and clinical characteristics (e.g., stage) with on pain outcomes via linear probability models. These analyses are underpowered, but will be used to explore potentially meaningful differences and estimate a possible effect size and conduct sample size calculations for a future randomized clinical trial.

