**23. ECONOMIC BURDEN TO SUBJECTS**

**24. PROCESS TO DOCUMENT CONSENT IN WRITING**

**25. DRUGS AND DEVICES**

**26. REFERENCES**

## 1.0 STUDY SCHEMA

## 2.0 INTRODUCTION

### 2.1 STUDY OVERVIEW

In this single arm pilot study, patients with advanced solid tumors and moderate-to-severe pain who are not already on high-dose opioids will be prospectively assigned to early referral to an anesthesia-trained interventional pain management specialist. Specialists all practice at the Brigham and Women's Hospital or its affiliated clinics (e.g., at [name], Faulkner Hospital, or Foxboro). These clinicians have a strong affiliation with the Dana-Farber Cancer Institute, and have extensive experience in managing cancer pain with a variety of interventional pain management procedures (e.g. celiac or hypogastric plexus blocks, intrathecal TDD).

Patients will be evaluated for interventional pain management strategies (including, but not limited to, nerve blocks and intrathecal TDD); they will be followed longitudinally with frequent reassessment and management guided by a standardized treatment pathway. This pathway is designed to make the intervention transferrable and ultimately scalable if it is proved effective.

Patients will be followed for 4 months with monthly surveys, and the option to report daily symptoms using a HIPPA-compliant pain-tracking smartphone application. Study staff will also complete structured chart abstractions at end-of-study to assess pain management interventions, opioid use, and healthcare utilization (e.g. hospitalizations/ED visits for pain), and survival.

Primary outcomes of this pilot study will relate to feasibility and acceptability, including recruitment and retention rates, number of completed interventional pain management consultations, the types of interventions offered and the proportion of patients accepting those interventions, and patients' satisfaction with the intervention. We will also explore time trends in clinically relevant outcomes including pain severity/interference, physical functioning, QOL, opioid dose, healthcare utilization and survival.

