### **3.0 OBJECTIVES**

There are three main objectives of this pilot study. Among patients with advanced solid malignancies who have moderate-to-severe cancer pain

1. Determine the feasibility of early referral for consideration of interventional pain management strategies
2. Determine the proportion of participants who are candidates for, and who ultimately receive at an interventional pain procedure
3. Determine patients' satisfaction with their pain management care

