### **6.2. Selection of Instruments**

*Feasibility:* As the primary goal of this study is to assess feasibility of the early intervention pain management intervention, our study team will track the following measures of feasibility

- Feasibility of recruitment: we will track the number of patients screened, the number approached, the proportion who consent to the study (and reasons for study refusal)
- Feasibility of the intervention: we will track the following
  - o Proportion of participants who undergo a consultation with an interventional pain specialist, and the proportion who do so within the target timeframe of 4-weeks
  - o Proportion of participants who are offered an interventional pain procedure, and the type of procedure offered (e.g. nerve block, steroid injection, epidural or intrathecal pump)
  - o Proportion of participants offered a procedure who accept the procedure, who undergo that procedure, and the timeframe of the procedure
  - o Proportion of patients who receive more than one pain intervention
- Feasibility of study assessments: We will keep track survey response rates and reason for non-completion
- Feasibility of retention: We will track the number of patients who complete the study, and reasons for drop-out

PROTOCOL TITLE: Randomized Clinical Trial of Early Intervention Pain Management for Patients with Advanced Cancers  
Version 4.0, [October 27, 2023]

**Survey assessments** will occur at baseline, 2-months, and 4-months. Measures are selected because we expect them to be covariates, primary or secondary outcomes of a future efficacy study.

*Pain severity:* pain severity will be assessed by averaging the least/average/worst pain rating from the Brief Pain Inventory (BPI) short-form (0-10 numeric rating scale, NRS). *Pain interference:* interference of pain on patients' general activity, mood, walking ability, work, relationships, sleep, and enjoyment of life will also be assessed by the BPI short-form (0-10)

*Quality of life:* will be assessed with the Functional Assessment Cancer Therapy: General (FACT-G) including its physical wellbeing, social/family wellbeing, emotional wellbeing, and functional wellbeing subscales.

*Anxiety and depression:* will be measured using the 4-item PROMIS depression short-form, and 4-item PROMIS anxiety short form

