### 7.3. Data Collection:

Three survey assessments (at baseline, 2-months, and 4-months) will assess future outcomes and covariates needed to plan a future randomized clinical trial, including patients' pain, functional wellbeing, and quality of life. The daily symptom reporting using a smartphone platform will enable

PROTOCOL TITLE: Randomized Clinical Trial of Early Intervention Pain Management for Patients with Advanced Cancers  
Version 4.0, [October 27, 2023]

exploratory longitudinal analyses of response to pain procedures. Structured chart abstractions will assess treatment compliance, opioid prescribing, changes in pain management, and healthcare utilization (i.e. hospitalization, ED visits).

Survey assessments: Patient will complete surveys at baseline, 2 months and 4 months. We anticipate pre-post differences in pain severity scores from baseline to 4 months to be our future primary outcome in a randomized clinical trial. 4 months is a relevant timeframe, because we anticipate it will be sufficient for a patient to be evaluated and treated with at least one interventional pain procedure, and any needed secondary procedures if response is insufficient.

The baseline survey will assess socio-demographics, characteristics and severity of pain, symptom burden and quality of life, and psychological characteristics known to influence pain (e.g. pain catastrophizing, perceived stress, anxiety, depression, sleep). Subsequent surveys will be brief and will focus on pain severity, functional interference, and quality of life.

7.3.1. Structured chart abstractions: A study assistant will abstract clinical characteristics at baseline (e.g. tumor type and location of metastases, date of diagnosis, current treatment). At the end of study, the RA will also conduct a detailed abstraction to evaluate the following (see appendices BA and BB):

- Any interventional pain management procedures, and dates of procedures
- Opioid doses (MMEDs) and dates of medication changes
- Unplanned and planned hospitalizations for pain
- Emergency department visits for pain
- Survival (which will be augmented by the National Death Index, which is integrated into the DFCI research database OnCORE through an existing process)

7.3.2. Smartphone based symptom reporting: \* As described in section 6.2, this is not applicable to patients recruited to the study after April 4th, 2023.

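### Section 9 labels pre-post pain severity the primary outcome of a feasibility pilot, and plans to size a randomized trial from uncontrolled pain models in app users

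*Combined protocol and SAP*

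**What the plan says.** **What is primary.** Section 2.1 says: "Primary outcomes of this pilot study will relate to feasibility and acceptability, including recruitment and retention rates". It places pain severity among the outcomes whose time trends will be explored. The first objective in Section 3.0 is to "Determine the feasibility of early referral for consideration of interventional pain management strategies"; the other two concern candidacy for and receipt of a procedure, and satisfaction. None is a change in pain. Section 9 opens its analysis text with "The primary purpose of our analysis is to examine feasibility and acceptability of the intervention" and gives three benchmarks (80%, 50%, 80%).

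**The conflicting label.** Later in the same section: "Pre-post differences in pain severity (primary outcome) will be examined using a one-sample t-test". A significance level of p<0.05 is set for the analyses in general.

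**The likely intent.** Section 6.2 says of the survey measures: "Measures are selected because we expect them to be covariates, primary or secondary outcomes of a future efficacy study". Section 7.3 anticipates "pre-post differences in pain severity scores from baseline to 4 months to be our future primary outcome in a randomized clinical trial".

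**The planning use.** The last paragraph of Section 9 fits linear regressions to the smartphone pain data, adjusted for baseline, to "explore the effect of the intervention on pain trajectories", and explores moderators. It concedes that these analyses are underpowered, but says they will be used to "estimate a possible effect size and conduct sample size calculations for a future randomized clinical trial".

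**The concern.** Read literally, Section 9 gives the pilot two primary outcomes. Only the unintended one carries a hypothesis test; the benchmarks are to be reported with 95% confidence intervals. A report that follows Section 9 could present a significant or null primary result on pain beside the feasibility results that are the study's actual endpoints.

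The planning use raises a separate issue. An RCT is sized on the difference between its arms. This study has one arm, and its pain models can show only how pain changed in patients who were all referred. Conceding low power deals with imprecision. It does not deal with the missing comparator, and neither does adjusting for baseline. If the within-patient change became the RCT's target difference, that trial could be mis-sized.

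**Working it through.** No figure in the plan can be reproduced on this point. The 31 participants come from projected clinical volume, and Section 9 declines a power calculation and gives no SD, correlation or expected change. The check is therefore mainly a comparison of texts.

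**Step 1: the label.**

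| Place | Status of pain severity | Status of feasibility |
|---|---|---|
| 2.1 | Explored as a time trend | Primary outcomes |
| 3.0 | Not an objective | First objective |
| 6.2 | Measure for a future efficacy study | Primary goal |
| 7.3 | Primary outcome of a future RCT | – |
| 7.3.2 | Among the primary/secondary outcomes, without *future* | – |
| 9 | Primary outcome, t-test | Primary purpose, three benchmarks |

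Sections 2.1, 3.0, 6.2 and 7.3 agree with one another. The label in Section 9 is the outlier, and Section 7.3.2 shares the loose wording. No decision rule refers to the t-test.

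**Step 2: what the pain models can estimate.** Section 6.1 describes a single-arm design. Observed change = any treatment effect + regression to the mean + other analgesic changes + disease course. Only the first term belongs in an RCT target difference, and one arm cannot separate it from the rest. Entry requires a pain score of at least 4 (Section 4.2), so participants are selected on a score closely related to the outcome. The same decomposition applies whether change is measured from referral or around a procedure.

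**Step 3: whose data.** Under Section 6.2 app reporting is optional and was not offered to those recruited after April 4, 2023. The trajectory data are therefore a self-selected, early-recruited subset of the 31. Section 6.2 also says that app summary reports go to oncologists before visits to support medication adjustments. The app is thus a co-intervention in the data meant to supply the effect size.

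**Step 4: what the pilot can supply.** An SD can be estimated from one arm, with 95% limits of sqrt((n−1)/χ²) times the estimate:

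- n = 31: sqrt(30/46.979) = 0.80 and sqrt(30/16.791) = 1.34.
- n = 23 (25% missing, an assumption; 31 × 0.75 = 23.25): sqrt(22/36.781) = 0.77 and sqrt(22/10.982) = 1.42.

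**Step 5: imputed values must be kept out.** Section 9 imputes by last observation carried forward (LOCF). Illustration, all inputs assumed: true baseline-to-4-month correlation 0.70, equal means and variances, and 25% of 4-month scores replaced by the baseline score.

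- Apparent correlation = 0.25 × 1 + 0.75 × 0.70 = 0.775.
- With zero mean change, the variance of change is multiplied by 0.75. The SD of change is multiplied by sqrt(0.75) = 0.866, a fall of about 13%.

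Both distortions would make a later trial look easier to power than it is.

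**The case against.** The strongest reply has four parts.

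1. *The label is a slip that the document resolves elsewhere.* This stands. It limits the first part to a wording correction. The p<0.05 level is also general to Section 9 and not attached to the pain sentence.

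2. *The last paragraph of Section 9 is openly exploratory and speaks only of a possible effect size.* This stands in part. A reader might infer that the observed pre-post change will be entered directly as the RCT's between-arm difference, but the text does not say so. It does name effect-size estimation and sample size calculation as the use, and it sets no limit for the missing comparator.

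3. *The word intervention there may mean a specific pain procedure.* Sections 7.1, 7.3 and 7.3.2 support that reading. It is a reason to keep the procedure-response analysis. A contrast around a dated procedure is still uncontrolled, so the planning objection is unchanged.

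4. *The limits of the app data are already disclosed.* The cutoff and the optional use are stated in several sections. The paragraph that uses the data for planning does not carry those limits through.

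A further tempting inference is that selection on pain makes a false-positive t-test likely. The documents do not support it. The baseline survey appears to be separate from screening, pain must have persisted for at least 2 weeks, worsening disease would push scores the other way, and LOCF from baseline pulls change towards zero. The net direction is unknown.

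**Conclusion.** The point holds in two parts of unequal weight. The primary-outcome label on pain severity in Section 9 is a labelling error: it contradicts the rest of the document, but no success rule depends on it and the feasibility endpoints are untouched. The plan to derive an RCT effect size and sample size from single-arm app models is wrong as written, because those models do not estimate a between-arm difference and rest on a selected subset exposed to a co-intervention. That conclusion follows from the design and needs no numerical assumption. The documents give nothing from which to determine how large the bias is or which way it runs. It should be corrected, and the correction is confined to wording.

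**What to change.** **Label.** In Section 9, replace *(primary outcome)* with *(anticipated primary outcome of the future RCT; exploratory here)*. In Section 7.3.2, insert *future* before the reference to primary/secondary outcome assessments. State that the pilot's primary outcomes are the feasibility and acceptability outcomes of Section 2.1, including recruitment and retention, with the three Section 9 benchmarks as the stated targets. Report pain change as a mean with 95% CI, treat any p-value as exploratory, and make no efficacy claim.

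**Planning use.** In the last paragraph of Section 9, keep the trajectory and procedure-response analyses, but describe them as uncontrolled within-patient change in opt-in app users. Replace the effect-size use with a statement that:

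- single-arm changes will not by themselves set the RCT target difference;
- the pilot will supply the SD and baseline-to-4-month correlation from observed, not LOCF-imputed, survey data, with confidence intervals based on the number observed;
- the pilot will also supply attrition and consultation rates;
- the target difference will be justified as a clinically important between-arm difference.

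**Cost.** Text changes in Sections 7.3.2 and 9, with no new data or visits. The study gives up an efficacy headline for pain and a pilot-derived effect size.

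### Carrying the last observation forward is the only missing-data rule for the pre-post tests, with no rule for deaths and a partly outdated app clause, so the pain-change estimate can be biased in either direction

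*Combined protocol and SAP*

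**What the plan says.** All of the following is in section 9 of the combined protocol and SAP unless another section is named.

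- Missing data: "Missing data will be imputed using a last observation carried forward principle, which will be greatly enhanced by the inclusion of smartphone symptom tracking". No other method, missingness assumption or sensitivity analysis is given. Section 7.3.2 adds that app scores will fill in incomplete survey outcomes, but gives no algorithm.
- Analyses that use the filled-in data: "Pre-post differences in pain severity (primary outcome) will be examined using a one-sample t-test", and "One-sample t-tests will also examine pre-post differences in pain interference scores, QOL scores" together with other scales and opioid dose.
- Analysis set: "Analyses will be conducted using an intent-to-treat analysis".
- Deaths: section 9 will report "the proportion alive at end-of-study" and provides for mortality follow-up. It does not say how a death before month 4 enters the pain-change analysis.
- App availability: section 7.1 makes the app surveys optional. Sections 6.2, 7.1, 7.3.2 and 23 say the app was not available to participants recruited after April 4, 2023. The app clause in section 9 carries no such limit.
- Use of the result: section 7.3 anticipates "pre-post differences in pain severity scores from baseline to 4 months to be our future primary outcome in a randomized clinical trial".

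**The concern.** For a participant without app data, the rule leaves two possible substitutes for a missing 4-month pain score. One is the 2-month score. The other, if that is missing too, is the baseline score, which sets the change to exactly zero. Neither measures pain at 4 months. Read literally with intent-to-treat, a participant who died before month 4 also receives a 4-month pain score.

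The direction of the error cannot be known in advance. Early loss, or loss because of high pain, pulls the estimate toward no change. Waning benefit, or worsening among those lost, overstates benefit. The rule also keeps 31 values in the test however many were observed, so the reported precision does not show the lost information. At stake is the pilot's estimate of the quantity expected to be the primary outcome of the later randomized trial.

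**Working it through.** **Inputs.** From the documents: 31 participants (sections 4.3 and 9), surveys at baseline, 2 and 4 months, and no app data after the cut-off. The documents give no SD, correlation, effect size, attrition or app uptake, and 31 rests on clinical volume, so there is no planned figure to reproduce. Assumed for illustration: SD 2.0 at each visit, correlation 0.6, true change -2.0, no app data for anyone, and 10, 20 or 33% missing at 4 months (33% is an upper scenario).

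**1. What a carried score represents.** Section 7.1 sets windows of weeks 7-13 and 15-19. A carried 2-month score is therefore 15 - 13 = 2 to 19 - 7 = 12 weeks older than the score it replaces. Section 7.2 aims for consultation within 4 weeks and a procedure ideally within 2 more, so week 6. A week-7 score can come one week after that. Section 7.3 justifies 4 months partly because it leaves time for second procedures, which a carried score can predate.

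**2. Mean by arithmetic, loss unrelated to pain, 20% missing.** Let h be the loss probability in each of the two intervals. (1 - h)² = 0.80 gives h = 0.1056. Lost before month 2: 0.1056 (change 0). Lost after month 2: 0.8944 × 0.1056 = 0.0944 (2-month change carried). Observed: 0.80.
- Means 6, 4, 4: 0.80 × (-2) + 0.0944 × (-2) + 0 = -1.79.
- Means 6, 5, 4: 0.80 × (-2) + 0.0944 × (-1) + 0 = -1.69.

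**3. Simulation.** 4000 replicates. In the pain-related rows, the logit of loss rises by 0.5 per point of last observed pain. Entries are the mean change (coverage of a nominal 95% interval) at 10 / 20 / 33% missing.

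| Loss; means | Carried forward | Observed cases |
|---|---|---|
| Unrelated; 6, 4, 4 | -1.89 (0.938) / -1.80 (0.901) / -1.64 (0.790) | -1.99 (0.958) / -2.00 (0.953) / -2.00 (0.948) |
| Unrelated; 6, 5, 4 | -1.84 (0.926) / -1.69 (0.843) / -1.48 (0.649) | -1.99 (0.961) / -2.00 (0.955) / -1.99 (0.946) |
| Pain-related; 6, 4, 4 | -1.78 (0.894) / -1.58 (0.735) / -1.32 (0.430) | -1.95 (0.947) / -1.90 (0.942) / -1.83 (0.928) |
| Pain-related; 6, 5, 4 | -1.77 (0.883) / -1.54 (0.710) / -1.27 (0.406) | -1.95 (0.948) / -1.91 (0.945) / -1.86 (0.938) |

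A separate run at 20% missing gave -1.55 to -1.79 with coverage 0.72 to 0.91, which agrees within simulation error.

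**4. The benign case.** With all loss after month 2 and means 6, 4, 4, carrying forward gives -2.00 with coverage about 0.95 if loss is unrelated to pain. If loss is pain-related it gives -1.94 / -1.89 / -1.85 with coverage 0.945 / 0.941 / 0.916.

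**5. The opposite direction.**
- Suppose 6 of 31 are missing and in truth worsened by 1.5 points. Benefit is overstated by 6/31 × 1.5 = 0.29 if baseline is carried. If a 2-month change of -1.0 is carried, it is overstated by 6/31 × 2.5 = 0.48.
- Suppose benefit is -1.5 at 2 months and 0 at 4 months, with losses after month 2 unrelated to pain (SD 2, correlation 0.5). At 20% missing the carried mean is 0.20 × (-1.5) = -0.30, and p<0.05 occurs in 12% of simulated trials. At 30% it is 0.30 × (-1.5) = -0.45, and p<0.05 occurs in 21%. The nominal rate is 5%.

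**6. Interval width.** The SD of change is 2 × √(2 × (1 - 0.6)) = 1.79. With all 31 observed, the width is 2 × 2.042 × 1.79/√31 = 1.31. With 25 observed, it is 2 × 2.064 × 1.79/√25 = 1.48. Carrying forward gives 1.25 to 1.32, about the complete-data width. The true SD of the carried-forward mean divided by its t-test standard error is 0.99 to 1.02. Coverage with the bias removed is 0.94 to 0.96.

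**The case against.** **Weight.** This is a feasibility pilot. None of the three objectives in section 3.0 is pain change, section 2.1 says such trends will be explored, and benchmarks 1 and 2 do not depend on this rule. That stands and limits the importance of the point. In the tabulated scenarios p<0.05 still occurred in at least 97% of replicates, so the damage there is to the estimate and not to the test result.

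**Loss may be small.** Eligibility requires a prognosis over 6 months and a completed baseline survey. Surveys can be done remotely, and payment comes with the final survey. These features should reduce loss, but cannot exclude death or non-response in advanced cancer.

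**The app clause is not void.** Earlier recruits who opted in could have recent scores to carry, which shortens the gap. The clause is out of date only for later recruits and for earlier ones who did not opt in. Assuming no app data for all 31 is therefore the extreme case.

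**Observed cases can be biased too.** If those lost are 2 points worse at month 4 and completers change by -1.5, then with 20% lost (half before month 2) the truth is -1.5 + 0.20 × 2 = -1.10. Carrying forward gives 0.90 × (-1.5) = -1.35 and observed cases give -1.50. This stands, and is why a shifted-score analysis is needed.

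**Stronger readings that the documents do not support:**
- That the interval is too narrow as a separate defect. Step 6 shows that the under-coverage is bias. Section 9 also promises 95% intervals only for the feasibility proportions.
- That the rule would turn a missed satisfaction benchmark ("At least 80% of patients will be satisfied with the quality of care received in the interventional pain management clinic") into a met one. No deciding survey is named, and a 2-month rating is a real rating of care.
- That depression and anxiety change would be zero for everyone because Table 3 lists those scales at baseline only. Section 7.1 says the later survey largely repeats the baseline one. This is a question about the schedule.
- That this t-test sizes the next trial. Section 9 links the aim to "estimate a possible effect size and conduct sample size calculations for a future randomized clinical trial" to the app-trajectory and moderator analyses, so any such use of the t-test is an inference.

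**Conclusion.** The concern holds as a moderate point that the plan should address. The only stated rule can misestimate 4-month pain change in either direction, it gives a literal 4-month score to participants who have died, and the support it claims from the app is missing for some of the sample.

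Under the stated assumptions and 20% missing, the estimate falls short of a true -2.0 by about 0.2 to 0.45 points, with coverage of 0.72 to 0.91. In the other direction, benefit is overstated by about 0.3 to 0.5 points in the worked cases. The rule is unbiased only in a narrow case: all loss after month 2, unrelated to pain, with equal 2- and 4-month means. The interval is about as wide as if all 31 scores had been seen, so it hides the lost information, but it is not otherwise miscalibrated.

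These sizes rest on assumed SD, correlation, effect and attrition, and on no app data. The absence of a death rule and the outdated clause rest on the text alone.

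**What to change.** In section 9, replace the carry-forward sentence, including its app clause, with:

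> Change from baseline to 4 months will be estimated with a 95% CI from observed surveys, without carrying scores forward and without assigning any score after death. The numbers alive with a survey, alive without a survey and died will be reported at each wave. For pain severity, sensitivity analyses will be (a) last observation carried forward, (b) a likelihood-based mixed model using all observed baseline, 2- and 4-month surveys, and (c) missing 4-month scores of living participants shifted 1, 2 and 3 points toward worse pain.

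The plan should also name the starting value for the shift in (c); the prediction from (b) would serve. With 6 of 31 missing and alive, those shifts move the mean by 6/31 × 1, 2 and 3 = 0.19, 0.39 and 0.58 points. The report should say that the main estimate describes participants alive and responding at 4 months, and that (b) treats scores after death as missing at random, which is why it is not the main analysis.

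In section 7.3.2, confine the use of app scores to a sensitivity analysis in participants recruited before April 4, 2023 who used the app.

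The cost is one replaced sentence, one edited clause and a little more analysis, with no new data collection. The interval becomes wider, about 1.47 against 1.3 points at 20% missing under the assumptions above.
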